Study protocol

**Sealed Therapeutic Shoe vs. Total Contact Cast as Treatment of Diabetic
Foot Ulcers: a Multicenter RCT**

Clinical Trial Registration Number: Unique Protocol ID: 18RS6667

Date: 9 September 2019

Background

Approximately 19-34 % of all people with diabetes will at some time in life develop a diabetic foot ulcer (DFU).¹ People with diabetes are especially prone to develop foot ulcers because of different diabetic complications, especially angiopathy and peripheral neuropathy.

The DFUs are often hard to heal and the treatment is long-lasting. The DFUs result in lower physical and mental quality of life and affects social relationships.² The treatment is also very costly,^{1,3} it has been estimated that 25-50 % of diabetic inpatient care is related to DFUs.⁴ Despite extensive treatment, all DFUs do not heal but some end in amputation. People with diabetes are at a 25-fold risk of amputation and every 20 second a person somewhere in the world has the foot amputated because of diabetes.⁵ 85 % of these amputations are preceded by a foot ulcer⁶ and many of these ulcers and amputation could have been prevented.⁷

Total contact cast (TCC) as gold standard treatment of DFUs

Plantar DFUs often are the result of a combination of foot deformities that increase plantar pressures when the person walks and that the person keeps walking despite high pressure and ulcers because he or she has lost sensation in the feet because of sensory neuropathy. Literature reviews and international guidelines^{8,9} recommend non-removable knee-high offloading devices, for example, a total contact cast (TCC) to treat plantar DFUs, as this offloads the ulcer from mechanical loading all day and night. Still, TCC is not accepted by all patients and is contraindicated in a number of cases because of negative side-effects. Most of these side-effects are the consequences of immobilizing the ankle joint, which impairs gait and results in lower ambulatory activity. For example, side-effects include reduction of joint flexibility, weight gain, muscle atrophy, sick leave from work and social isolation.¹⁰ In addition, a TCC can give secondary ulcers why weekly visits to the hospital is necessary to change casts. For these reasons, TCC is only used for a minority of the patients for whom it could be beneficial, despite being the gold standard treatment.¹¹

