The participants will be randomized to treatment with sealed therapeutic shoe or TCC. The randomization will be stratified for ulcer size (smaller or bigger than 1 cm^2 , ulcer size calculated as longest diameter*longest perpendicular diameter) and study center, and use random permuted blocks of randomly varying size.

Recruitment of participants

People who fulfill the inclusion criteria and not the exclusion criteria will be given oral and written study information and asked about whether they are interested in participating in the study. Those who agree will sign an informed constant to participate.

Intervention group, sealed therapeutic shoe: A prosthetist/orthotist will try out new therapeutic shoes to the participants and make individual insoles after casts of the feet. There will a limited number of shoe types to choose between and the procedure and material for the insole production will be standardized. The ulcer will be offloaded by adjusting the insoles with the help of plantar pressure measurement using the F-scan system (Tekscan, Boston, MA, USA). The “seal” of the shoe consists of a soft plastic strip (Bracelok, DJO Nordic, Malmö) that have to be broken to remove the shoe.

[figure not shown]
Control group, TCC: The participants will be treated with TCC, applied in a standardized manner. Participants in this group will also receive shoes and insoles, according to the same protocol as above, before TCC treatment is initiated to be comparable to the other group in the long-term follow-up after healing, when both groups will use shoes and insoles to prevent reulceration.

Both groups will visit the cast technician 1-2 times/per week depending on the status of the ulcer. The cast technician will change dressings, note whether the seal has been broken (for the intervention group), change casts (for the control group), photograph and document ulcers and complications, and ask participants if they have experienced any issues with the treatment. After this, a new dressing is applied, and the shoe is sealed (intervention group) or

a new cast is applied (control group). Participants will use a cover on the shoe or cast while taking a shower, and for the intervention group a cover will also be used when sleeping. Both groups will receive written information about potential complications and contact information to the clinics.

Data collection

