2.5 STATISTICAL INTERIM ANALYSES AND STOPPING GUIDANCE

One interim analysis will be conducted after the primary outcome (proportion of healed ulcers at 12 weeks) has been observed in 30 participants in each study arm. The analysis will be conducted according to the intention-to-treat (ITT) approach, that is, all participants randomized will be analyzed according to their intended study group. If a two-sided Chi-square test demonstrates a statistically significant difference between the groups on the 0.001 level (relative risk, risk difference and odds ratio (OR) with confidence intervals (CI) will also be calculated) recruitment of new participants will be stopped but the follow-up of participants who already are enrolled in the study will continue. If the Chi-square test is not significant (that is, $p > 0.001$), recruitment of new participants will continue as planned. The significance level will not be adjusted due to the interim analysis as only one interim analysis is conducted.

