3.3 ANALYSIS POPULATIONS

The primary outcome (ulcer healing) will be analyzed both on the ITT dataset, that is, on all randomized participants, and on the per protocol dataset, including only patients who were exposed to the intended intervention at least 80% of the treatment days, as judged per above (point 3.2). Secondary outcomes (including adverse events and adverse device effects) will only be analyzed on the ITT dataset.

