4.3 RECRUITMENT

Information required by the CONSORT flow diagram will be collected and presented: number of patients screened, number who were excluded (per reason) and number who declined to participate, number of patients randomized, number of participants who were allocated to each study group, number who received the allocated intervention and number who did not receive the allocated intervention (per reason and study group), number who discontinued intervention or were lost to follow-up (per reason, per follow-up visit and per study group), number who were analyzed and excluded from analysis (per reason and study group).

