5.3 SAFETY ASSESSMENTS

5.3.1 ADVERSE EVENTS

Adverse events that are judged to be related to the offloading devices (shoe or TCC) will be classified as adverse device effects (ADE) and serious adverse device effects (SADE).³² ADE include, but are not limited to, skin abrasions, blisters, sleep disturbances, issues with gait and balance, etc. SADE include, but are not limited to, new foot ulcers that result in amputation (major amputation = above ankle, minor amputation = below ankle), sepsis, etc.

Averse events that are not related to the offloading devices are classified as adverse events (AE) and serious adverse events (SAE).³² AE include, but are not limited to, skin abrasions or new foot ulcers on the contralateral foot and not related to the device, etc. SAE include, but are not limited to, death, amputation, onset of acute Charcot foot, sepsis, etc. (not related to the offloading device). However, in accordance with previous studies on similar patient populations, not all AE and SAE will be included as the patient population suffers from multiple co-morbidities and therefore a high incidence of illness and hospital admissions unrelated to the DFU and offloading devices can be expected.³³ Therefore, all ADE and SADE will be assessed, but only certain types of AE and SAE that are of particular interest, such as, amputation, death and onset of acute Charcot foot.

ADE, SADE, AE and SAE will be assessed with the aid of questionnaires, CRF, photographs of ulcer and skin, and patient files.

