6.1.2 ANALYSIS OF THE SECONDARY ENDPOINT(S)

The secondary analyses are not dependent on the findings of the primary endpoint. No adjustment for Type 1 errors will be used as only one or a few statistical tests will be conducted for each secondary endpoint.

The secondary endpoints are time to healing and measures listed in Table 1. Each secondary endpoint is measured between one and five occasions during the study. The ITT dataset will be used for all analyses of secondary endpoints. Adjusted analyses will only be conducted for certain secondary endpoints that are of particular interest.

Time to healing will be compared between the study groups using survival analysis. Kaplan-Meier survival curves will be produced for the two study groups with median healing times and 95 % CI. Participants for whom the ulcer has not healed will be treated as censored and their date of trial exit or date of last available assessment will be used to calculate their duration in the trial. Hazard ratio with

95% CIs will be presented. Treatment effect will be explored using a Cox proportional hazards model including stratification factors (ulcer area and depth at baseline, periphery artery disease and infection grade) initially.

Survival analysis as above (but without adjustment) will also be used to compare ulcer recurrence after healing between the study groups. Recurrence rates at 12 months after healing will also be compared.

The analysis of the other secondary endpoints will be conducted according to scale level (nominal, ordinal or interval; Table 1) and compared at each time point (base-line, 4 weeks into treatment and 1, 6 and 12 months post-treatment) using the ITT dataset without adjustment for covariates: t-tests for ordinal and interval data if the assumptions of the t-test is fulfilled (normal distribution and equal variances), otherwise Wilcoxon rank sum test will be used. The Chi-squared test or generalized linear regression method will be used for nominal scale data. For each comparison both exact p-values and two-sided 95% CI will be reported.

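### Adverse device effects are analysed only by randomised group, so non-exposure, receipt of the other device and time in the device are ignored; a supplementary table by device received is needed

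*SAP*

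**What the plan says.** SAP 3.3 sets the analysis set for safety: "Secondary outcomes (including adverse events and adverse device effects) will only be analyzed on the ITT dataset". SAP 6.1.2 repeats the rule for every secondary endpoint: "The ITT dataset will be used for all analyses of secondary endpoints".

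The ITT set is described in SAP 3.3 for healing: "The primary outcome (ulcer healing) will be analyzed both on the ITT dataset, that is, on all randomized participants". SAP 2.5, writing of the interim analysis, gives the grouping rule: "all participants randomized will be analyzed according to their intended study group". SAP 6.1.3 reports safety in the treatment period as number and percentage per study group, compared by a chi-square test with two-sided intervals.

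The endpoint itself is tied to a device. SAP 5.3.1 reads: "Adverse events that are judged to be related to the offloading devices (shoe or TCC) will be classified as adverse device effects". Serious adverse device effects (SADE) are defined in the same way.

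No exposed-only, as-received or safety set is defined. The per-protocol set (at least 80% of treatment days on the intended intervention) and the sensitivity analyses in SAP 6.1.8 cover healing only.

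**The concern.** Each ADE is judged against a device but tabulated by allocation. The two agree only if everyone receives the allocated device. The SAP expects that some will not: section 3.2 names refusal and administration of the wrong intervention, section 4.3 counts non-receipt, and section 4.4 lists withdrawal before the intervention is given. These are reported as counts and never reach the safety analysis.

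Two consequences follow from the text. A participant who never had the allocated device cannot have an effect of it, yet stays in its denominator. A device effect in someone who received the other device would be counted in the randomised arm.

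A third does not depend on any departure from allocation. According to the protocol's data collection section, treatment ends at healing, and SAP 6.1.2 compares time to healing between the groups. Time in the device may therefore differ by arm, and a percentage per arm does not separate the rate of harm from the length of wear.

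At stake are the treatment-period safety comparison (Objective 2) and the question in SAP 6.1.5 whether non-removable devices are safe in people with impaired circulation or infected ulcers. A percentage that mixes exposed and unexposed people need not be the risk of either device.

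**Working it through.** **Plan's own figures.** There are none to reproduce. The documents give no ADE risk, switching rate or non-exposure rate. The only design figures used here are group sizes: 150 participants at 1:1 gives 75 per arm, and SAP 2.3 allows a minimum of 56 per arm. Everything else is assumed.

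**Formula.** Let pT and pS be the ADE risk on TCC and in the shoe, x the share of the TCC arm that receives the shoe instead, and u the share of the TCC arm that receives neither device and so has no device effect. Switching is taken as unrelated to risk, and the shoe arm as fully exposed to the shoe. The risk shown by ITT is then

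TCC arm = pT × (1 − x − u) + pS × x; shoe arm = pS.

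Example: pT = 30%, pS = 15%, x = 10%, u = 0 gives 0.9 × 0.30 + 0.1 × 0.15 = 0.285, and 28.5 − 15 = 13.5 points.

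| pT | pS | x | u | TCC arm by ITT | ITT difference (TCC − shoe) | Difference between devices |
|---|---|---|---|---|---|---|
| 30% | 15% | 10% | 0 | 28.5% | 13.5 | 15 |
| 30% | 15% | 20% | 0 | 27% | 12 | 15 |
| 30% | 15% | 30% | 0 | 25.5% | 10.5 | 15 |
| 30% | 15% | 0 | 20% | 24% | 9 | 15 |
| 20% | 40% | 0 | 20% | 16% | −24 | −20 |
| 20% | 40% | 10% | 10% | 20% | −20 | −20 |
| 20% | 40% | 20% | 10% | 22% | −18 | −20 |
| 30% | 30% | 0 | 10% | 27% | −3 | 0 |

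The first four rows shrink the difference. In the fifth, with the shoe riskier, the gap widens from 20 to 24 points. In the sixth, the two errors cancel (0.8 × 0.20 + 0.1 × 0.40 = 0.20). In the last, equal devices show a 3-point difference; if 10% of the shoe arm were also unexposed, both arms would show 27% and it would vanish. The problem is symmetric: cast effects in a shoe-arm participant would be counted under the shoe.

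**The same in counts.** Take 75 per arm, pT = 30%, pS = 10%, x = 10%, u = 10%. In the TCC arm, 75 × 0.8 = 60 wear the cast and 60 × 0.30 = 18 have an ADE; 7.5 wear the shoe and 0.75 have an ADE; 7.5 wear neither.

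- By ITT: (18 + 0.75)/75 = 25%, a difference of 15 points from the shoe arm's 10%.
- By device received: 18/60 = 30%, a difference of 20 points.

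Power at two-sided 5% is 68% by ITT and 85% by device received; with 56 per arm it is 55% and 74%. The higher figures hold only if switching is unrelated to risk.

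**Time in the device.** If ADEs arise at a constant rate r per week over T weeks, the chance of at least one is 1 − exp(−rT). Two devices with the same r but different T then give different percentages. Events per device-week estimate r directly.

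**The case against.** ITT is a legitimate answer to Objective 2. It keeps the randomised comparison and counts what follows from being assigned a cast that some people will refuse. The SAP also reports non-receipt, discontinuation, non-adherence and wrong intervention by arm, so a reader can judge how much dilution is possible. This stands, and is why ITT should remain the randomised analysis.

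Three stronger readings are tempting, and the documents support none of them.

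- *TCC participants who leave the cast will wear the study shoe, and its harms will be charged to TCC.* The protocol says: "Participants in this group will also receive shoes and insoles, according to the same protocol as above, before TCC treatment is initiated". The sentence goes on to give the purpose, which is comparability after healing, and nothing says that a cast-leaver moves to the sealed shoe. The background remark "Still, TCC is not accepted by all patients and is contraindicated in a number of cases because of negative side-effects" describes ordinary practice, not people who agreed to randomisation. SAP 6.1.3 also covers only the treatment period, whose end after refusal is not defined, so later events might not be counted at all.
- *ITT always pulls the arms together.* It does so in some of the scenarios above and not in others.
- *The comparison by device worn should be the main analysis.* It is not randomised, and leaving a device may itself be caused by an ADE. Assigning events to whatever is worn at onset can also reverse the error: a gait problem caused by the cast but noticed after a change would be charged to the shoe. SAP 5.3.1 rests on judged relatedness, and attribution should follow that.

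**Conclusion.** The concern holds as a gap in the plan, not as a demonstrated bias. SAP 3.3 excludes any analysis of device effects among those who received a device, although the endpoint is defined by the device and the SAP foresees departures from allocation.

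The size cannot be stated from the documents. Under the assumed 30% and 15% risks, 10% to 30% switching costs 1.5 to 4.5 points of a 15-point difference, and 20% non-exposure in the TCC arm costs 6 points. Under other assumptions the difference is unchanged, widened by 4 points or created from nothing (3 points). With no departures from allocation, only the device-time point remains. The change is worth making because it is cheap and removes an explicit restriction, not because a large error has been shown.

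**What to change.** - **SAP 3.3:** keep ITT as the randomised comparison for all safety outcomes. Remove the word *only* as it applies to ADE and SADE, and define a supplementary safety set of participants who received a study device, grouped by device received.
- **Attribution:** assign each ADE and SADE to the device it was judged related to under SAP 5.3.1. State how a participant who received both devices is handled, for example in the denominator of each with weeks divided between them, and when device time starts and stops.
- **SAP 6.1.3:** beside the ITT table, report number, percentage and events per device-week for this set, labelled supplementary and non-randomised.
- **SAP 6.1.5:** give the same table for the circulation and infection sub-groups.

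The sample size does not change. The cost is SAP wording and one further table. The cast technician already sees participants once or twice a week and records broken seals, cast changes and complications, and the 80% rule for the per-protocol set already calls for exposure days. The documents do not say that the device concerned is recorded for each ADE, so a case report form field may be needed. Device time may also be incomplete for participants who refuse treatment and stop attending. The remaining downside is the possibility of informative switching, which the ITT table alongside keeps in view.

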4 STUDY POPULATION

4.1 SCREENING DATA

The following summaries will be presented for all screened patients:

Enrolment: the number of patients screened, the number of patients recruited, and the reason for non-recruitment.

4.2 ELIGIBILITY

All patients attending the multidisciplinary diabetic foot teams at the study centers during the screening period will be assessed for eligibility.

Inclusion criteria: at least 18 years old, diagnosed diabetes mellitus (all types) and foot ulcer under metatarsal heads. A foot ulcer is here defined as “a break of the skin of the foot that includes minimally the epidermis and part of the dermis.”³⁰

Exclusion criteria: large ulcers (covering 3-5 metatarsal heads), toe pressure or TcPO₂ <30 mmHg, infection of IWGDF grade 3 (if uncontrolled or treatment has not been administered) or IWGDF grade 4, life expectancy <1 year, active Charcot foot, need of custom-made shoe, and inability to read or write Swedish. In addition, people will be excluded where dementia, language- or other communication difficulties, active alcohol or substance abuse, or other factors increase the risk that adverse events or adverse device effects will not be noted or reported, if the person does not have adequate social support.

The eligibility data will be summarized as number of patients screened, number of patients who fulfilled the inclusion criteria, and the number of the patients fulfilling the inclusion criteria that were excluded due to violating each exclusion criterion or who declined to participate. In addition, the number of ineligible patients randomized, if any, will be reported, with reasons for ineligibility.

4.3 RECRUITMENT

Information required by the CONSORT flow diagram will be collected and presented: number of patients screened, number who were excluded (per reason) and number who declined to participate, number of patients randomized, number of participants who were allocated to each study group, number who received the allocated intervention and number who did not receive the allocated intervention (per reason and study group), number who discontinued intervention or were lost to follow-up (per reason, per follow-up visit and per study group), number who were analyzed and excluded from analysis (per reason and study group).

4.4 WITHDRAW / FOLLOW-UP

There are several timings of possible withdrawal/lost to follow-up: before base-line assessment, before the intervention has been administered, during the intervention period, and before each follow-up assessment. Reasons include, but are not restricted to, clinical reasons, death, refusal to continue treatment or follow-up, unable to make contact with the participant, etc.

Number of participants, reasons and timing of withdrawal/lost to follow-up will be presented by intervention arm in a CONSORT flow diagram (point 4.3)

5 STUDY ASSESSMENTS

5.1 BASELINE PATIENT CHARACTERISTICS

Baseline characteristics that will be summarized include: sex, age, education level, living conditions (living alone, with partner, children, etc.), diabetes type and duration, glycemic control, body mass index (BMI), history of previous foot ulcers and amputations, foot deformities, index foot ulcer characteristics (site, area, depth, duration, infection grade), number of active ulcers, use of tobacco, peripheral artery disease (toe pressure, TcPO₂), and neuropathy (assessed with Ipswitch Touch Test and Vibratip).

Categorical data will be summarized as n (%).

Continues data will be summarized as mean (standard deviation).

5.2 EFFICACY ASSESSMENTS

5.2.1 PRIMARY EFFICACY ENDPOINT

Primary efficacy endpoint is ulcer healing at 12 weeks, defined as complete epithelialization which is maintained for a minimum of 14 days (as required by the US Food and Drug Administration, FDA)³¹. Ulcer healing will be assessed by the cast technician at the local hospital who redress the DFU, approximately 1-2 times per week (depending on the status of the DFU) in both groups. The cast technician will also photograph the DFU so it can be assessed by another person, blinded to group allocation.

